11.1 Adverse events

All AEs will be coded using the Medical Dictionary for Regulatory Activities (MedDRA) Version 22.0 (or later).

Adverse events will be grouped by system organ class (SOC) and PT and summarised by treatment. The summary tables will present the number and percentage of subjects with AEs and number of events, by SOC and by PT for each treatment group.

All AE summaries will be restricted to Treatment-emergent adverse events (TEAEs) only.

A treatment emergent adverse events (TEAE) is defined as any AE with an onset date on or after the first dose of study treatment if the AE was absent before the first dose of study treatment, or pre-existing medical condition worsens after the first dose of study treatment.

For the summaries of AEs, subjects who experience the same AE (in terms of the MedDRA SOC and

QMS Document Name: Statistical Analysis Plan	Page 19 of 33
QMS No (include version ref): STF-015-GL.02	Document date: 09JUL2019
CONFIDENTIAL	

PT) more than once will only be counted once for that event in the number of subjects but all occurrences of the same event will be counted in the number of events.

For analysis, at AE level, the worst severity and the strongest relationship to trial treatment will be assigned to the AE if the severity and relationship changes overtime for the AE with the same AE ID. At subject level, a subject with the same AE term being reported multiple times, the maximum severity and the strongest relationship to trial treatment will be tabulated.

Study drug related TEAEs are defined as TEAEs with definitely, probably, or possibly relationship with study drug

Nature and severity of adverse event (AEs) and number of patients with AEs will be analysed as primary endpoint in part A and secondary endpoints of Part B.

An overview table of TEAEs will be provided detailing the number and percentage of subjects along with the number of reported events with

- Any TEAE
- TEAEs by severity (Mild, Moderate, Severe)
- Any TEAE related to study drug
- Any serious TEAE
- Any serious TEAE, related to study drug
- Any TEAE leading to discontinuation of study drug
- Any TEAE leading to death

Summary tables will also be provided for TEAEs, TEAE by severity, study drug related TEAEs, TEAEs leading to discontinuation of study drug, and TEAEs leading to death, detailing the number and percentage of subjects and number of events by MedDRA SOC (ordered by frequency) and PT (ordered by frequency).

Separate patient listings will be provided for AEs, SAEs, AEs leading to study drug discontinuation, and AEs leading to death. The listings will also include subjects enrolled but not randomised.

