9 ADVERSE EVENTS

An AE is defined as any untoward medical occurrence in a patient administered a pharmaceutical product during the course of a clinical investigation. An AE can therefore be any unfavorable and unintended sign, symptom, or disease temporally associated with the use of a study drug, whether or not thought to be related to the study drug.

Each AE will be collected from the signing of the ICF until the follow-up/end-of-study visit. Adverse events that are identified at the last assessment visit (or the early termination visit) must be recorded on the AE eCRF with the status of the AE noted. All events that are ongoing at this time will be recorded as ongoing on the eCRF. If the Investigator indicates the AE is “probably”, “possibly”, or “definitely” related to the study drug, the AE must be followed until they are resolved or medically stable, or until reasonable attempts to determine resolution of the event are exhausted. The investigator should use his/her discretion in ordering additional tests as necessary to monitor the resolution of such events.

The procedures specified in [Section 9.4](#) are to be followed for reporting SAEs.

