10.6 Safety Analysis

All safety analysis will be performed on the SAS for both Part A and Part B.

Adverse events will be coded by System Organ Class and Preferred Term using the current version of MedDRA. Incidences of TEAEs (ie, events that started after 1st dose of the study drug or worsened in severity after 1st dosing), will be presented by dose group. Incidences of TEAEs will also be presented by maximum severity and relationship to study medication.

Safety data will be summarized through appropriate data tabulations, standard descriptive statistics, and graphical presentations. For each continuous laboratory parameter, results will be categorized as low, normal, or high based on the laboratory normal ranges. Frequencies and percentages will be presented by dose group for patients who had a shift to low and for patients who had a shift to high from baseline to any post-dosing assessment.

The association of AEs, clinical laboratory tests, vital sign measurements with the actual dosing of the study drug or systemic exposure of LT5001 drug product may also be explored. If appropriate, statistical modeling will be performed to further characterize the associations mentioned above. All out-of-range and clinically significant laboratory results will be identified in patient data listings. The number and percentage of patients in each dose group with normal and abnormal physical examination results will be presented for evaluations at baseline and final visit.

For each body system, changes in the patients' findings from baseline to final visit (no change, normal to abnormal, or abnormal to normal) will be tabulated for each dose group.

Application site examination (observed and change from baseline) will be summarized by time point using appropriate descriptive statistics.

The number and percentage of patients reporting any treatment-emergent AE will be tabulated by system organ class and preferred term (coded using MedDRA). Treatment-emergent AEs will be further classified by severity and relationship to treatment.

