Appendix III: Partial Date Conventions

- Algorithm for Treatment Emergence of Adverse Events:

START DATE	STOP DATE	ACTION
Known	Known	If start date < study med start date, then not TEAE. If start date \geq study med start date, then TEAE.
	Partial	If start date < study med start date, then not TEAE. If start date \geq study med start date, then TEAE.
	Missing	If start date < study med start date, then not TEAE. If start date \geq study med start date, then TEAE.
Partial, but known components show that it cannot be on or after study med start date	Known	Not TEAE
	Partial	Not TEAE
	Missing	Not TEAE
Partial, could be on or after study med start date	Known	If stop date < study med start date, then not TEAE. If stop date \geq study med start date, then TEAE.
	Partial	Impute stop date as latest possible date (i.e. last day of month if day unknown or 31st December if day and month are unknown), then: If stop date < study med start date, then not TEAE. If stop date \geq study med start date, then TEAE.
	Missing	Assumed TEAE
Missing	Known	If stop date < study med start date, then not TEAE. If stop date \geq study med start date, then TEAE.
	Partial	Impute stop date as latest possible date (i.e. last day of month if day unknown or 31st December if day and month are unknown), then: If stop date < study med start date, then not TEAE. If stop date \geq study med start date, then TEAE.

QMS Document Name: Statistical Analysis Plan	Page 32 of 33
QMS No (include version ref): STF-015-GL.02	Document date: 09JUL2019
CONFIDENTIAL	

START DATE	STOP DATE	ACTION
	Missing	Assumed TEAE.

QMS Document Name: Statistical Analysis Plan	Page 33 of 33
QMS No (include version ref): STF-015-GL.02	Document date: 09JUL2019
CONFIDENTIAL

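### SAP 11.1 and SAP Appendix III define treatment-emergent adverse events differently, and each departs from protocol 10.6 in one case

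*SAP*

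**What the plan says.** Three places define which adverse events are treatment-emergent.

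- **Protocol 10.6** (the synopsis agrees) counts "events that started after 1st dose of the study drug or worsened in severity after 1st dosing". It sets no condition on what happened before dosing.
- **SAP 11.1** has two limbs. The first is "any AE with an onset date on or after the first dose of study treatment if the AE was absent before the first dose". The second is "or pre-existing medical condition worsens after the first dose of study treatment".
- **SAP Appendix III** decides by date. When the start date is known, the rows read "If start date \geq study med start date, then TEAE" and "If start date < study med start date, then not TEAE". Neither row mentions an earlier episode or worsening.

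The definition has wide reach. SAP 11.1 states: "All AE summaries will be restricted to Treatment-emergent adverse events (TEAEs) only". The Part A primary endpoint and the Part B secondary safety endpoint, the nature, severity and number of patients with AEs, are analysed in that section. Events before dosing are on record, since protocol section 9 says: "Each AE will be collected from the signing of the ICF until the follow-up/end-of-study visit". SAP 2.1 reports no departure from the protocol analysis, and the SAP does not say whether 11.1 or Appendix III governs where they differ.

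**The concern.** A programmer who follows SAP 11.1 and one who follows Appendix III can produce different TEAE tables from the same data, and each can differ from what the protocol promises.

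The first conflict concerns recurrence. Screening may last up to 28 days (protocol 5.1.2), so an event can appear and resolve before the first dose and return afterwards. Protocol 10.6 counts the new episode. The extra condition in SAP 11.1 can be read to exclude it unless it is worse than before.

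The second conflict concerns worsening. An event that is ongoing at first dose and then worsens is counted by protocol 10.6 and by the second limb of SAP 11.1. If the record keeps its original start date, Appendix III rejects it. SAP 11.1 expects such records, because it lets severity change within one AE ID: "the worst severity and the strongest relationship to trial treatment will be assigned to the AE if the severity and relationship changes overtime".

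Both conflicts bear on the Part A primary endpoint. They also bear on the interim analysis, which SAP section 13 says follows this SAP and which the DSMB reviews before Part B.

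**Working it through.** The plan states no figure on this point, so there is nothing to reproduce. The check applies each rule to the event histories that matter, with all dates known.

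**Inputs.** The three definitions above, and the Part A arm sizes of 12 (LT5001) and 6 (placebo) from SAP 3.3.

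**Notation.** P: present at some time before first dose. O: still present at first dose. N: a record with onset on or after first dose. W: severity after first dose worse than before.

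**Rules.**
- Protocol 10.6: N or W.
- SAP 11.1, with absence read as never present before dosing (reading 1): (N and not P) or W.
- SAP 11.1, with absence read as not present at first dose (reading 2): (N and not O) or W.
- Appendix III: N.

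The worsening limb of SAP 11.1 is assumed to cover a recurrence graded worse than the earlier episode.

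| History | Protocol 10.6 | SAP 11.1, reading 1 | SAP 11.1, reading 2 | Appendix III |
|---|---|---|---|---|
| 1. New event | TEAE | TEAE | TEAE | TEAE |
| 2. Resolved before dosing, recurs at same or lower severity | TEAE | **not TEAE** | TEAE | TEAE |
| 3. Resolved before dosing, recurs worse | TEAE | TEAE | TEAE | TEAE |
| 4. Ongoing at dosing, worsens, original start date kept | TEAE | TEAE | TEAE | **not TEAE** |
| 5. Ongoing at dosing, worsens, new record opened | TEAE | TEAE | TEAE | TEAE |
| 6. Ongoing and unchanged | not TEAE | not TEAE | not TEAE | not TEAE |

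Only histories 2 and 4 split the rules. History 2 depends on how SAP 11.1 is read. If the condition is applied to the single record, it adds nothing, because a record with post-dose onset was absent before dosing by construction. History 4 does not depend on any reading of SAP 11.1.

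**Size per patient.** A patient whose event is lost changes that preferred term's incidence by 100/n points.
- LT5001, Part A: 100/12 = 8.3 points.
- Placebo, Part A: 100/6 = 16.7 points.
- Part B, per arm: 100/45 = 2.2 points with the protocol's 45, or 100/30 = 3.3 points with the SAP's 30.

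The any-TEAE incidence moves by the same amount only if the patient has no other TEAE.

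**Severity, a smaller matter.** The worst-grade rule in SAP 11.1 has no start point. It misreports a TEAE only when one record spans first dose, was graded higher before dosing, eased, and then worsened again; for example severe, then mild, then moderate after dosing. With a known start date, Appendix III as written never lets such a record become a TEAE, so the case becomes live once the worsening rule is added there.

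**The case against.** A reader might infer that SAP 11.1 removes all recurrences from every AE table. The documents do not support that, for four reasons.

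- Recurrences at higher severity are kept by the worsening limb. Only those at the same or lower severity are at risk.
- The condition can be read as not present at first dose, in contrast to the pre-existing conditions of the next limb. That reading agrees with the protocol, and the consistency statement in SAP 2.1 favours it.
- Appendix III belongs to the same SAP and keeps these events by date alone. What the SAP contains is an unresolved disagreement, not a settled exclusion.
- Local skin findings have a second route. SAP 11.6 tabulates application-site and ROAT results by ICDRG grade and treatment group. The patient listings are not stated to be limited to TEAEs.

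A reader might also infer a sizeable rate of loss. Suppose a background event affects 20% to 50% of patients independently in each four-week window. Then 0.20 × 0.20 = 4% to 0.50 × 0.50 = 25% have it on both sides of first dose. This uses the maximum screening length, whereas the synopsis expects about one week. At constant hazard, one week gives (1 − 0.80^(1/4)) × 0.20 = 1.1% to (1 − 0.50^(1/4)) × 0.50 = 8.0%, before requiring that the event resolve before dosing. All of these rates are assumptions; none comes from the trial.

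It can be said for Appendix III that it only sorts dates and leaves the definition to SAP 11.1. But it is labelled as the algorithm for treatment emergence, and its first rows cover fully known dates, where no date needs resolving.

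These objections limit the first conflict to one subset under one reading. They do not remove it, since the choice is left to the programmer, and they do not touch the second conflict.

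**Conclusion.** The point holds as an inconsistency between two SAP rules and the protocol. SAP 11.1, read literally, can drop a recurrence at the same or lower severity that protocol 10.6 and Appendix III count. Appendix III drops a worsened event with a known pre-dose start that protocol 10.6 and SAP 11.1 count. The second conflict is the clearer one.

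The number of affected patients cannot be derived from the documents. The effect per patient is large in Part A only because the arms have 12 and 6 patients. The conclusion rests on two assumptions: for recurrence, that the SAP 11.1 condition is applied to the event rather than the record and over the whole pre-dose period; for worsening, that the record keeps its original start date.

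**What to change.** Use the protocol 10.6 definition in both places.

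1. In SAP 11.1, delete the condition that the event was absent before first dose. State that a new episode with onset on or after first dose is a TEAE even if an earlier episode resolved before dosing.
2. In Appendix III, add that an event starting before first dose is a TEAE if its severity worsens afterwards.
3. As a minor addition, for a record that spans first dose, take TEAE severity from the grades recorded on or after first dose.

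The cost is a few sentences in the SAP and matching program logic. The protocol need not change. Item 3, like the worsening rule, needs the timing of grade changes within a record. TEAE counts may rise slightly, in line with the protocol, and the consistency statement in SAP 2.1 would then be true on this point.

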11.2 Deaths

Deaths will be presented as listing in detail by using death report form of CRF.

11.3 Vital signs

The following vital signs will be measured at every study visit and reported for this study.

- Temperature(°C)
- Respiratory rate (breaths/min)
- Systolic blood pressure/SBP (mmHg)
- Diastolic blood pressure/DBP (mmHg)

QMS Document Name: Statistical Analysis Plan	Page 20 of 33
QMS No (include version ref): STF-015-GL.02	Document date: 09JUL2019
CONFIDENTIAL	

- Pulse Rate (mmHg)

Observed value and absolute change from baseline to each visit will be summarized by descriptive statistics (number of subjects with data, number of subjects with missing values, mean, SD, median, minimum, and maximum) by treatment group.

11.5 Physical examination

The following physical examinations will be evaluated by the investigator as Normal, abnormal NCS, Abnormal CS at every study visit and reported for this study.

- General appearance
- Skin
- Head and neck (eyes, ears, nose, mouth, and throat)
- Chest and Lung
- Heart
- Abdomen
- Extremities
- Neurologic System
- Other

The following summaries will be provided:

A summary of the number and percentage of subjects with normal, abnormal but not clinically significant, and abnormal clinically significant physical examination findings, by body system, treatment group, and visit.

For each physical examination, shift from baseline to each post-baseline protocol scheduled time point's evaluation, will be summarised by treatment group, using frequency tabulations.

A by-subject listing of physical examination results will be provided.

11.6 Application site examination

The application site evaluation will include dermatitis, pruritus, paresthesia, erythema, dryness, vesicles, irritation, papules, burning assessed by ICDRG scale. ICDRG scale consist of negative(-), doubtful reaction(+/?), weak positive reaction(+), strong positive reaction(++) , extreme positive reactions(+++), irritant reaction (IR). Application site examination (observed and change from baseline) will be summarized as number and percentage of subjects by each treatment group.

7-days ROAT assessed by ICDRG scale will also be summarized as number and percentage of subjects by each treatment group

12 Pharmacokinetics

Pharmacokinetics analysis will be performed only in Part A.

Pharmacokinetic parameters will be listed by subject and treatment using the pharmacokinetic analysis set (PKAS)

All calculations for PK parameters will be based on actual dosing and sampling times recorded during the study. Considering the actual dose received by each patient may vary, the PK parameter will be adjusted by dividing to the actual dose of each patient.

QMS Document Name: Statistical Analysis Plan	Page 22 of 33
QMS No (include version ref): STF-015-GL.02	Document date: 09JUL2019
CONFIDENTIAL	

Blood concentrations that are below the limit of quantification (BLQ) prior to the first measurable concentration will be set to zero, BLQ values that are between measurable concentrations will be set to missing, and BLQ values that occur at the end of the profile (after the last quantifiable concentration) will be set to missing.

All PK parameters will be summarized as descriptive statistics (n, arithmetic mean, standard deviation (SD), CV%, minimum, median, and maximum, geometric mean, and geometric CV%). Missing values will be omitted from the calculation of descriptive statistics

Scatter plots of individual adjusted PK parameters ($C_{trough}/$ Actual Dose) and non-adjusted PK parameters (C_{trough}) versus time for LT5001 drug product will be produced on log-log scales using the PKAS.

13 Interim Analyses

Interim analysis and DSMB:

After Part A completion, the interim analysis for all data will be done.

Statistical analysis for interim analysis will be performed based on this SAP.

DSMB will review interim analysis and give comments on safety or any medical concern to determine whether the study continues or not. Also, DSMB will give comments for LT5001 drug product daily dose and regimen for Part B. Sponsor will make the final decision in an unblinded fashion.

14 Statistical Analyses for Safety Monitoring

The statistical analysis for safety monitoring is specified in a separate DMC charter.

15 Applicable Software

All analyses will be conducted using SAS® Version 9.4 or higher in a secure and validated environment. Figures may be prepared using the same version of SAS®.

16 Abbreviations

UP	uremic pruritus
AE	adverse event
BMI	body mass index
BUN	blood urea nitrogen
CFR	Code of Federal Regulations
CRU	clinical research unit
CRO	contract research organization
C_{trough}	lowest observed blood concentration prior to next application
DSMB	data and safety monitoring board
eCRF	electronic case report form

QMS Document Name: Statistical Analysis Plan	Page 23 of 33
QMS No (include version ref): STF-015-GL.02	Document date: 09JUL2019
CONFIDENTIAL	

[figure not shown]
EOS	end-of-study
FU	follow-up
GCP	Good Clinical Practice
HBV	hepatitis B virus
HCV	hepatitis C virus
HIV	human immunodeficiency virus
ICF	informed consent form
ICH	International Council for Harmonisation
Itch NRS	itch numerical rating scale
NRS	numerical rating scale
MedDRA	Medical Dictionary for Regulatory Activities
PK	pharmacokinetic(s)
SAE	serious adverse event
SAS	safety analysis set
SD	standard deviation
SOP	standard operating procedure

[figure not shown]
17 References

1. LT5001-101 Protocol V3.0/ Date: 17 Jan 2020
2. LT5001-101 Subject Case Report Forms V2.0/ Date: 20 Feb 2020
4. Statistical Principles for Clinical Trials E9. ICH Harmonised Tripartite Guideline
5. Good Clinical Practice: Consolidated Guideline E6. ICH Harmonised Tripartite Guideline

[figure not shown]
18 Appendices

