2 SCHEDULE OF ASSESSMENTS AND PROCEDURES

[figure not shown]
CONFIDENTIAL

CONFIDENTIAL

Table 2.2 Schedule of assessments and procedures- Part B

CONFIDENTIAL

CONFIDENTIAL

Table 2.3 Pharmacokinetic Sampling Schedule – Part A

Visit	Study Day	Time Relative to 1 st Study Drug Administration (Hour)	Pharmacokinetic Blood Sample
0	-28 to -1	Not applicable	Not applicable
1	1	0 (predose)	X
2	3	48 ± 4 (trough)	X
3	6	120 ± 4 (trough)	X
4	8	168 ± 4 (trough)	X
5	15	336 ± 4 (trough)	X
6	22	504 ± 4 (trough)	X
7	29	672 ± 4 (trough)	X
8	36	Not applicable	Not applicable

Pharmacokinetic samples will be collected as close to the nominal time point as possible. Allowable windows for PK collection will be ± 4 hours for all trough samples.

LIST OF ABBREVIATIONS

Abbreviation	Definition
UP	uremic pruritus
AE	adverse event
BLQ	below the limit of quantification
BMI	body mass index
BUN	blood urea nitrogen
CFR	Code of Federal Regulations
CNS	central nervous system
CRU	clinical research unit
CRO	contract research organization
C _{trough}	lowest observed blood concentration prior to next application
DSMB	data and safety monitoring board
eCRF	electronic case report form
EOS	end-of-study
FDA	Food and Drug Administration
FU	follow-up
GCP	Good Clinical Practice
HBV	hepatitis B virus
HCV	hepatitis C virus
HIV	human immunodeficiency virus
ICF	informed consent form
ICH	International Council for Harmonisation
IEC	independent ethics committee
IRB	institutional review board
Itch NRS	itch numerical rating scale
NOAEL	no observed adverse effect limit
NRS	numerical rating scale
MedDRA	Medical Dictionary for Regulatory Activities
OTC	over-the-counter
PK	pharmacokinetic(s)
SAE	serious adverse event
SAS	safety analysis set
SD	standard deviation
SOP	standard operating procedure
SRM	study reference manual
ULN	upper limit of normal

CONFIDENTIAL

STUDY ADMINISTRATIVE STRUCTURE

Sponsor:

Lumosa Therapeutics Co., Ltd.

CONFIDENTIAL

[REDACTED]
[REDACTED].

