10.5 Pharmacokinetic Analysis Part A (only)

The following PK parameters will be determined for LT5001 drug product:

C_{trough} Lowest observed blood concentration prior to next application

All calculations for PK parameters will be based on actual dosing and sampling times recorded during the study. Considering the actual dose received by each patient may vary, the PK parameter will be adjusted by dividing to the actual dose of each patient

Adjusted PK parameter = C_{trough} / Actual Dose

The actual dosing in each patient will be determined by subtract the weight of each returned study drug from the initial weight (T_0). In addition, the original blood PK parameter (without dose adjustment) versus time will also be analyzed.

Pharmacokinetic parameters will be listed by subject and treatment using the SAS, and summarized by treatment using the pharmacokinetic analysis set (PKAS) and the following summary statistics: n, arithmetic mean, standard deviation (SD), CV%, minimum, median, and maximum. Geometric mean and geometric CV% will also be presented for all PK parameters.

CONFIDENTIAL

Scatter plots of individual adjusted PK parameters (C_{trough} / Actual Dose) and non-adjusted PK parameters (C_{trough}) versus time for LT5001 drug product will be produced on log-log scales using the PKAS.

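### SAP Section 12 codes a BLQ trough by its position in the patient's series, so flat exposure can appear to rise and the rule creates zeros that the planned geometric statistics cannot take (minor)

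*SAP*

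**What the plan says.** SAP Section 12 and the synopsis of the protocol (Pharmacokinetics Parameters) give the same three-part rule. For early and intermediate results the text reads: "prior to the first measurable concentration will be set to zero, BLQ values that are between measurable concentrations will be set to missing". The third part concerns a patient's late results: "BLQ values that occur at the end of the profile (after the last quantifiable concentration) will be set to missing". SAP Section 12 adds: "Missing values will be omitted from the calculation of descriptive statistics".

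Protocol Table 2.3 lists a pre-dose sample and six post-dose samples at 48, 120, 168, 336, 504 and 672 hours (Days 3, 6, 8, 15, 22 and 29). Each post-dose sample is labelled a trough, and the table's note says "Allowable windows for PK collection will be ± 4 hours for all trough samples".

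The one visible parameter is C_trough, defined in Protocol Section 10.5 as "Lowest observed blood concentration prior to next application". The same section says that "the original blood PK parameter (without dose adjustment) versus time will also be analyzed" and that "Geometric mean and geometric CV% will also be presented for all PK parameters". The only output over time that is described in full is a scatter plot of individual values, which "versus time for LT5001 drug product will be produced on log-log scales using the PKAS".

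Nothing visible says how a zero enters a geometric mean, a geometric CV% or a log axis. A zero is not a missing value, so the omission sentence does not cover it.

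**The concern.** A rule for BLQ values at the end of a profile suits a single-dose curve with a declining tail. This schedule has no tail: a BLQ result on Day 29 is a steady-treatment trough like any other and is evidence of low exposure. Under the rule the same assay result counts as zero if it comes early and vanishes if it comes late. Early means are pulled down and later means pushed up.

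Pharmacokinetics are part of the Part A objective (Protocol Section 4.1), and the DSMB sees the available PK data beside the safety data before the Part B dose is decided (Protocol Section 5.1.1). A rise produced by the coding could be read as accumulation. Separately, the programmer would have to choose how to treat zeros in the geometric statistics, and the choices give different answers.

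**Working it through.** The plan states no figure on this point, so there is nothing to reproduce.

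**Inputs from the documents.** 12 active patients in Part A (synopsis, Sample Size); six post-dose troughs (Table 2.3); the BLQ rule and the omission of missing values (SAP Section 12).

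**Inputs assumed, because the documents do not give them.** The LLOQ, the share of samples BLQ, the lognormal shape and the between- and within-patient variability.

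**1. Example that needs no LLOQ.** Twelve patients are each BLQ at exactly one of the six visits, two per visit, and otherwise have a value of 10. Every visit then has the same data.
- Day 3: the two BLQ values precede any measurable value and become 0. Mean = (10 × 10 + 2 × 0)/12 = 8.3.
- Each later visit: the two BLQ values follow a measurable value and are deleted. Mean = (10 × 10)/10 = 10.0.
- Apparent rise: 10.0/8.3 = 1.2-fold, from coding alone. With LLOQ/2 throughout, every visit gives (100 + LLOQ)/12.

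**2. Direction in general.** Suppose every analysed patient has at least one quantifiable post-dose value. Then every Day 3 BLQ becomes 0 and every Day 29 BLQ is deleted, so the first-to-last change cannot be biased downward.

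**3. Size under flat lognormal exposure** (20,000 simulated active arms per setting; ranges run over keeping or excluding patients who are always BLQ). False ratio of mean C_trough, Day 29/Day 3:

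| Between/within log-SD | 2% BLQ | 10% BLQ | 30% BLQ | 50% BLQ |
|---|---|---|---|---|
| 0.8/0.6 | 1.02 | 1.10 | about 1.3 | 1.4-1.6 |
| 0.8/0.2 | 1.01 | 1.05 | 1.11-1.14 | 1.14-1.25 |
| 0.8/0.01 (almost no crossing) | 1.00-1.01 | 1.00-1.01 | 1.00-1.01 | 1.00-1.01 |

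Chance of seeing a ratio above 1.5 in one trial:
- 0.8/0.6: 12%, 18%, 35-37% and 47-58% at the four BLQ rates, against 10-11% with no censoring.
- 0.8/0.2: 0.1%, 0.5%, 3-6% and 8-20%.

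With 0.8/0.6 and no censoring, chance alone gives a 95% range of 0.53-1.92 for the ratio, so a 2-10% bias is small within one trial.

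**4. A uniform rule removes the trend.** At log-SDs 0.4/0.6 and 50% BLQ, excluding patients who are never quantifiable, the true mean is 1.37 LLOQ at every visit. The plan's rule gives 1.08, 1.39, 1.61, 1.77, 1.89 and 1.98. All-zero gives 1.08 throughout and LLOQ/2 gives 1.31 throughout.

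**5. Zeros in the geometric statistics.** Take 0, 0, 1.2, 1.5 and 2.0 with LLOQ = 1. The log form is undefined and the product form gives 0. Dropping zeros gives 3.6^(1/3) = 1.53. LLOQ/2 gives (0.5 × 0.5 × 3.6)^(1/5) = 0.98.

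For a lognormal with total log-SD 1.0, dropping a share p multiplies the geometric mean by exp[φ(z_p)/(1 − p)]:
- p = 10%: exp(0.1755/0.9) = 1.22
- p = 30%: exp(0.3477/0.7) = 1.64
- p = 50%: exp(0.3989/0.5) = 2.22

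Zeros need not be rare. At 10% BLQ, the chance that at least one of 12 patients is BLQ on Day 3 is 1 − 0.9^12 = 72%.

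**The case against.** The strongest reply is that the affected output is inferred. SAP Section 12 and Protocol Section 10.5 promise listings by subject and summaries by treatment; neither says by visit. The mock-up templates mentioned in SAP Section 5.1 are not visible. The one specified plot over time is on log-log scales, where early zeros cannot be drawn and later BLQ values are absent, so BLQ results are lost at all visits alike. A by-visit geometric mean of positive values likewise gave a Day 29/Day 3 ratio of 1.00 in every setting. If C_trough is a single value per patient, there is no trend over visits to distort. All this stands, and it confines the false trend to arithmetic summaries by visit. The templates could settle the layout, but they would not alter how SAP Section 12 codes the values.

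It also stands that n, minimum and subject listings are planned. In a by-visit table, a shrinking n and a Day 3 minimum of zero would alert a careful reader.

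Exposure need not be flat either: the application test adds drug in the first 7 days, and SAP Section 8.4 provides for patients who do not apply drug because they do not itch. This weakens any reading of accumulation but not the direction of the coding bias. With flat, doubling, halving and four-fold falling exposure, the average first-to-last bias was upward in all 36 settings tried. The dose-adjusted parameter was not simulated.

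A reader might infer that the rule always produces a rise. It does not. With no crossing of the LLOQ there is no trend. If BLQ values fall only on Days 6 and 8 after a measurable Day 3, the fitted slope is lowered while Day 29/Day 3 stays at 1.00. Single trials can also go the other way when patients who are always BLQ are kept as zeros.

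**Conclusion.** The concern holds in a limited form. The rule treats identical results differently by position, and this schedule gives no reason for that. If patients cross the LLOQ and arithmetic C_trough is summarised by visit, flat exposure will generally appear to rise. The rise is 2-10% at 2-10% BLQ and 30-60% at 30-50% BLQ with a within-patient log-SD of 0.6; it is 1-5% and 11-25% with a log-SD of 0.2; and it is at most about 1% when almost nobody crosses. These sizes rest on an assumed lognormal shape, BLQ rate and variability, and on the inferred layout.

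The gap on zeros does not depend on a by-visit layout: the rule creates values that the planned geometric mean, geometric CV% and log-log plots cannot take, and dropping them overstates the geometric mean.

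A reader might go further and conclude that the Part B dose decision is compromised or that exposure is hidden. The documents do not support that. Part A pharmacokinetics are descriptive in 12 active patients, the Part A primary endpoint is adverse events, the DSMB weighs PK data beside the safety data, and the usual error overstates later exposure. The priority is minor.

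**What to change.** In SAP Section 12 and the protocol synopsis:
- Replace the positional rule with one rule for every post-dose BLQ trough, for example LLOQ/2, or a censored-data estimate for the geometric statistics.
- Keep pre-dose BLQ at zero, and leave it out of the geometric statistics and log plots.
- Show the number and percentage BLQ beside each summary.

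The cost is wording and minor programming, with no extra samples.

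The drawback is that any substitution is a convention. At total log-SD 1.0 the LLOQ/2 geometric mean is exp[p(z_p − ln 2) + φ(z_p)] times the truth: 0.98 at 10-30% BLQ, 1.05 at 50%, and exp[0.7 × (0.524 − 0.693) + 0.348] = 1.26 at 70%. The log-SD shrinks to 0.86 at 50% BLQ and 0.67 at 70%. A substituted constant divided by actual dose also varies only with dose. The percentage BLQ must therefore be shown, and the summaries read with caution when most values are BLQ.
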